**Use the treatment start date**

Patients with missing start dates are to be considered missing for all study treatment component related calculations and no imputation will be made. If start date is missing then end-date should not be imputed.

The following rules will be used for the imputation of the dose end date for ET:

If the dose end date is completely missing and there is no death date or withdrawal from consent date, the patient is considered ongoing. The cut-off date should be used as the last date of dose. If there is death date or withdrawal from consent date, then the dose end date will be the earlier of the death date and withdrawal from consent date. After imputation, compare the imputed date with start date, if the imputed date is < start date of treatment:

**Use the treatment start date**

#### 4.1.2 AE, ConMeds and safety assessment partial date imputation

**Table 4-1 Imputation of partial start dates (AE, CM) and assessments (LB, EG, VS)**

Missing Element	Rule
day, month, and year	
 
No imputation will be done for completely missing dates
 

day, month	
 
If available year = year of study treatment start date then                             
 
If stop date contains a full date and stop date is earlier than study treatment start date then set start date = 01JanYYYY
 
Else set start date = study treatment start date.
 
 
 
If available year > year of study treatment start date then 01JanYYYY
 
If available year < year of study treatment start date then 01JulYYYY
 

Missing Element	Rule
day	

• If available month and year = month and year of study treatment start date then

○ If stop date contains a full date and stop date is earlier than study treatment start date then set start date= 01MONYYYY.

○ Else set start date = study treatment start date.

• If available month and year > month and year of study treatment start date then 01MONYYYY

• If available month and year < month year of study treatment start date then 15MONYYYY

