### **On-treatment assessment/event and observation periods**

For adverse event reporting the overall observation period will be divided into three mutually exclusive segments, based on AE start date:

1. ***pre-treatment period***: from day of patient’s informed consent to the day before first administration of study treatment
2. ***on-treatment period***: from date of first administration of study treatment to 30 days after date of last actual administration of any study treatment (including start and stop date)
3. ***post-treatment period***: starting at day 30+1 after last administration of study treatment.

Safety summaries (tables, figures) include only data from the on-treatment period with the exception of baseline data which will also be summarized where appropriate (e.g. change from baseline summaries). In addition, a separate summary for death including on treatment and post treatment deaths will be provided. In particular, summary tables for adverse events (AEs) will summarize only on-treatment events, with a start date during the on-treatment period (***treatment-emergent*** AEs).

However, all safety data (including those from the post-treatment period) will be listed and those collected during the pre-treatment and post-treatment period will be flagged.

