**Table 4-2 Imputation of partial end dates (AE, CM)**

Missing Element	Rule (*= $\min$ (last study treatment date plus 30 days, death date, cut-off date, withdrawal of consent date))
day, month, and year	

No imputation will be done for completely missing dates

day, month	

If partial end date contains year only, set end date = earliest of 31DecYYYY or end date of the on-treatment period *

day	

If partial end date contains month and year, set end date = earliest of last day of the month or end date of the on-treatment period*

Any AEs and ConMeds with partial/missing dates will be displayed as such in the data listings.

Any AEs and ConMeds which are continuing as per data cut-off will be shown as 'ongoing' rather than the end date provided.

The above imputations are only used for analyses of time to and duration of AEs and concomitant medications. For completely missing end date, it will not be considered as an event date for duration of AE analysis.

The above rules will be used for imputation of AE end dates if AE start date is before last dose of study treatment. In this study, SAEs suspected to be related with study treatment or ET alone after EOT will continue to be collected. The imputation of end date of SAE during the post-treatment period will be based on the same rules by replacing end date of on-treatment period in above table with last contact date.

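### Table 4-1 accepts only a full stop date as proof of a pre-treatment end, so a year-only start with a month-year stop before treatment is imputed to begin after it ended

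*SAP*

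**What the plan says.** SAP section 4.1.2, Table 4-1, covers partial start dates of AEs and concomitant medications and partial dates of laboratory, ECG and vital-sign assessments. In the row where day and month are missing and the year is that of treatment start, there are two branches. The first is for records that ended before treatment: "If stop date contains a full date and stop date is earlier than study treatment start date then set start date = 01JanYYYY". The second is the fallback, and it takes in every record whose stop is partial, missing or not before treatment; there the start becomes the day on which study treatment began.

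Table 4-2 covers partial end dates of AEs and concomitant medications: "If partial end date contains month and year, set end date = earliest of last day of the month or end date of the on-treatment period".

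The text below Table 4-2 limits the use of both tables: "The above imputations are only used for analyses of time to and duration of AEs and concomitant medications". It also says that partial dates appear in listings as recorded.

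Section 2.1.1 sets the reporting periods: "For adverse event reporting the overall observation period will be divided into three mutually exclusive segments, based on AE start date". The pre-treatment period runs "from day of patient’s informed consent to the day before first administration of study treatment". AE summary tables "will summarize only on-treatment events, with a start date during the on-treatment period".

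**The concern.** The first branch is meant to recognise a record that was over before treatment. It does so only when the stop is known to the day. A stop known to the month can prove the same thing, yet it falls to the second branch, which places the start on the first treatment day. The rule discards recorded information and produces an impossible pair of dates.

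No later step corrects this. Section 4.1.1 compares imputed dose end dates with the treatment start date, but section 4.1.2 has no equivalent check for AEs or concomitant medications.

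Two things are at stake. In any duration analysis, the affected record has no valid duration. And if imputed starts are also used to assign AEs to periods, an event known to have ended before the first dose would enter the AE and special-interest tables, which serve the primary endpoint.

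**Working it through.** **Inputs.** The branch rules come from Table 4-1, the month-year end rule from Table 4-2, and period assignment from section 2.1.1. The SAP gives no formula for AE duration, so I use the inclusive count that section 2.4.1 uses for exposure: end − start + 1. The dates below are illustrative. I assume that the on-treatment period ends after the stop month, as it must when the stop month precedes treatment.

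**Step 1: apply both tables as written, AE start recorded as '2017'.**

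| Treatment start | Recorded stop | Imputed start | End date | End − start + 1 |
|---|---|---|---|---|
| 10-Apr-2017 | Mar-2017 | 10-Apr-2017 | 31-Mar-2017 | −10 + 1 = −9 |
| 15-Jun-2017 | Mar-2017 | 15-Jun-2017 | 31-Mar-2017 | −76 + 1 = −75 |
| 15-Jun-2017 | May-2017 | 15-Jun-2017 | 31-May-2017 | −15 + 1 = −14 |
| 15-Jun-2017 | 20-Mar-2017 | 01-Jan-2017 | 20-Mar-2017 | 78 + 1 = 79 |
| 15-Jun-2017 | Jun-2017 | 15-Jun-2017 | 30-Jun-2017 | 15 + 1 = 16 |

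The full stop date is handled properly. So is a stop in the treatment month, where the data cannot show that the event ended before treatment. The rule fails for month-year stops in earlier months.

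**Step 2: does it always fail there?** Let treatment start on a day in month k and the recorded stop month be m < k of the same year. The imputed start is the treatment start, which is on or after day 1 of month k. The imputed end is the last day of month m, which is before day 1 of month k. So start is always after end. The smallest gap is one day (treatment starts on the 1st, stop in the month before), where the inclusive duration is 0. In every other case it is negative.

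Counting all such pairs in a 365-day year, days in month × earlier months: 28×1 + 31×2 + 30×3 + 31×4 + 30×5 + 31×6 + 31×7 + 30×8 + 31×9 + 30×10 + 31×11 = 2,017 pairs. All are reversed. (That the total matches the year 2017 is a coincidence.)

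**Step 3: other rows.** Where only the day is missing, a month-year start with a month-year stop gives no reversal. The missing check does show elsewhere in Table 4-1. With treatment in June 2017, a start of '2016' becomes 01-Jul-2016 even if the stop is 20-Mar-2016, and a start of 'March 2017' becomes 15-Mar-2017 even if the stop is 10-Mar-2017. These stay before treatment, so only the order is wrong.

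**Step 4: period assignment.** Section 2.1.1 classifies AEs by start date and gives no rule for a partial start. In the affected case the imputed start is the first treatment day, which lies in the on-treatment period. The sentence below Table 4-2, however, confines imputed dates to time-to and duration analyses. Read together, the two places do not say how an AE with a partial start is classified.

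**Step 5: after the change.** For start '2017', stop 'March 2017' and treatment start 10-Apr-2017, testing 31-Mar-2017 against treatment start selects the first branch: start 01-Jan-2017, end 31-Mar-2017, duration 31 + 28 + 31 = 90 days, wholly before treatment.

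**The case against.** The strongest objection concerns consequences. A reader might infer that these AEs become treatment-emergent and distort the primary safety tables. The documents do not support that as a settled result, because the sentence below Table 4-2 appears to exclude that use. A reader might also expect a negative duration in the listings; the SAP says partial dates are shown there as recorded. Both points stand.

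It also stands that section 2.7.1 describes no time-to-onset or duration output for AEs. Its summaries are counts and percentages, plus a count of serious AE occurrences that compares a start with the prior end date. The SAP does not say whether imputed dates feed that count. So no specified result is shown to change.

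A further objection is that imputing end dates first would remove the reversal: 'March 2017' becomes 31-Mar-2017 and the first branch applies. That is true arithmetically, but the SAP states no such order and its wording points the other way. Asking whether a stop is a full date makes sense only for the recorded date, since after Table 4-2 every non-missing stop is full. The text below Table 4-2 also applies the AE end-date rules according to whether the AE started before the last dose, which needs a start date first.

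Finally, the case is narrow: start known only to the year, stop known to the month, both in the treatment-start year, the stop month wholly before treatment and, for AEs, onset after consent. That stands too. Concomitant medications are not tied to consent in this way, so the pattern could also arise there.

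**Conclusion.** The defect is real but minor. On its natural reading, Table 4-1 gives every record of this pattern a start after its own end, and section 4.1.2 has no check to catch it. Any duration computed from such a record is negative, or zero in the one-day-gap case.

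The effect on treatment-emergent counts is conditional. It arises only if imputed starts also drive the period assignment in section 2.1.1. That is plausible, since the SAP offers no other start date for these AEs, describes no AE duration output that would otherwise need the table, and builds the branches around treatment start. But it is not stated, and the limiting sentence speaks against it. If it did happen, each affected AE would move in one direction, from pre-treatment to treatment-emergent.

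The number of records cannot be derived from the SAP and is probably small. Only descriptive results are in play. The conclusion assumes that Table 4-1 is applied to the stop date as recorded.

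**What to change.** Make three changes to the SAP:

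1. In the row of Table 4-1 with day and month missing, reword the condition: 'If the latest possible stop date (the full date, or the last day of the recorded month) is earlier than study treatment start, set start date = 01JanYYYY.' For AEs only, use the informed consent date instead if it is later than 01JanYYYY and not after the stop. The limit to AEs matters because the table also covers concomitant medications, and a medication stopped before consent would otherwise be given a start after its stop.
2. Add below the table: 'An imputed start date may not be later than the recorded or imputed stop date.' This also catches the 01-July and 15th-of-month cases.
3. State whether imputed start dates decide treatment-emergent status, and bring section 2.1.1 and the sentence below Table 4-2 into line. If they do not, say how an AE with a partial start is classified.

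The cost is one reworded condition, one consistency check in the date program and one clarifying sentence. No new data are needed.

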### **Baseline**

For efficacy evaluations, the last non-missing assessment, including unscheduled assessments on or before the date of randomization is taken as “baseline” value or “baseline” assessment. In the context of baseline definition, the efficacy evaluations also include PRO and performance status.

For safety evaluations, the last available assessment on or before the date of start of study treatment is taken as “baseline” assessment.

For ECGs, the study requires triplicates per time point. The average of these measurements would be calculated for baseline. In case ribociclib/placebo dosing time is recorded on the date of first dose of study treatment along with the ECG, the last available assessment before the ribociclib/placebo start date/time will be used for baseline.

In rare cases where multiple measurements meet the baseline definition, with no further flag or label that can identify the chronological order, then the following rule should be applied: If values are from central and local laboratories, the value from central assessment should be considered as baseline. If multiple values are from the same laboratory or collected for ECGs or vital signs, then the last value should be considered as baseline. The last value refers to the one with a larger repeated sequence number recorded in the eCRF.

If patients have no value as defined above, the baseline result will be missing.

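### Table 4-1 of the SAP covers partial-dated lab, ECG and vital-sign records, contradicts the SAP's own limit on using imputed dates, and if applied can make an on-treatment value the baseline

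*SAP*

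**What the plan says.** Four parts of the SAP bear on this.

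- **Section 4.1.2, Table 4-1.** The heading gives the scope: "Imputation of partial start dates (AE, CM) and assessments (LB, EG, VS". When only the year is known and it equals the year of treatment start, the exception reads "If stop date contains a full date and stop date is earlier than study treatment start date then set start date = 01JanYYYY"; in every other case the rule is "Else set start date = study treatment start date". The row for a missing day alone has the same structure, using month and year.
- **Section 2.1.1, Baseline.** "For safety evaluations, the last available assessment on or before the date of start of study treatment is taken as" the baseline, so an assessment dated on the start day qualifies. If several values qualify and no flag or label shows their order, a central laboratory value beats a local one. Within one laboratory, or for ECGs and vital signs, the last value is used: "The last value refers to the one with a larger repeated sequence number recorded in the eCRF". For ECGs, where dosing time is recorded on the first-dose date along with the ECG, "the last available assessment before the ribociclib/placebo start date/time will be used for baseline".
- **Section 4.1.2, text after Table 4-2.** "The above imputations are only used for analyses of time to and duration of AEs and concomitant medications".
- **Sections 2.4.2, 2.7.3 and 2.7.4.** The primary endpoint includes laboratory and ECG abnormalities. Lab shift tables run from baseline to the worst later value. ECG changes, newly notable ECG values and most notable vital-sign criteria also refer to baseline.

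**The concern.** Moving a partial-dated adverse event to treatment start is cautious, because it brings the event into the on-treatment tables. The same move has a different effect on an assessment. The start date is the last day on which a safety assessment can serve as baseline, so a sample taken after treatment began can become the reference against which later samples are judged. It also stops counting as a post-baseline value.

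If that sample was abnormal, the patient loses an on-treatment abnormality and later values are compared with an already abnormal reference. The shift and change-from-baseline tables then understate what happened. The sentence after Table 4-2 would prevent this if taken literally, but it conflicts with the table heading, and a programmer has to choose between them.

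**Working it through.** The plan has no figure of its own to reproduce, so the check traces the rules through hypothetical records. All patient values and dates below are assumptions.

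**Step 1: which branch of Table 4-1 applies.** The exception needs a full stop date before treatment start. A lab sample, ECG or vital sign is a single time point and normally has no stop date (assumption). The default therefore applies and the imputed date equals the treatment start date.

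**Step 2: which record becomes baseline.** The rule takes the latest record dated on or before treatment start. A record placed on the start date is later than a pre-dose value dated on any earlier day, so it wins outright. The tie rules matter only when the true pre-dose value is itself dated on the start day.

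**Step 3: laboratory example.** Study treatment, including ribociclib, starts on 5 January. Neutrophils (10^9/L) are 3.0 on an earlier, fully dated day; 0.8 on 19 January, recorded with the day missing; and 1.2 as the worst remaining value. By the section 4.3 grades, 3.0 is grade 0 (at least 2), 0.8 is grade 3 (below 1.0 down to 0.5) and 1.2 is grade 2 (below 1.5 down to 1.0).

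| Handling of the 0.8 record | Baseline grade | Worst post-baseline grade |
|---|---|---|
| True date | 0 | 3 |
| Table 4-1 applied | 3 | 2 |
| Not imputed, record left out | 0 | 2 |

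**Step 4: ECG example, with no dosing time recorded.** Treatment starts on 6 September 2017. QTcF is 410 ms on 30 August, 475 ms on 20 September (date partial) and 470 ms on 4 October. The result is the same whether the day, or the day and month, are missing.

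- True date: baseline 410; largest change 475 − 410 = +65 ms, which meets the section 2.7.4.1 criterion of more than 60 ms.
- Table 4-1 applied: baseline 475; largest change 470 − 475 = −5 ms, so no increase is flagged.
- Not imputed, record left out: baseline 410; largest change 470 − 410 = +60 ms, which falls in the band above 30 and up to 60 ms.

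**Step 5: how many days can collapse onto the start date.** With the day missing, the count is the last day of the month minus the start day: 30 − 1 = 29 days for a 1 September start and 30 − 30 = 0 for a 30 September start. With day and month missing, it is the number of days left in the year: 363 for a 2 January start and 11 for a 20 December start (2017 calendar).

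**Step 6: direction.** Put the same three neutrophil values in another order: true baseline 1.2 (grade 2), partial-dated on-treatment value 3.0 (grade 0), later worst value 0.8 (grade 3). Table 4-1 now gives a shift of 0 to 3 where the true shift is 2 to 3. Here deterioration is overstated.

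**The case against.** The strongest counter-argument is the sentence after Table 4-2. It follows both tables, its reference to time-to analyses must include start dates and so Table 4-1, and its wording is exclusive. Read literally, an imputed assessment date never reaches baseline selection. This stands to the extent that the chain in steps 1 to 4 is conditional on the table being applied as headed. It does not settle the matter, because on that reading naming LB, EG and VS in the heading has no purpose and the plan has no rule for partial-dated assessments. Section 2.7.1 also lists no time-to or duration analysis of AEs, while section 2.1.1 assigns AEs to periods by start date. A programmer would thus have reason to use Table 4-1 beyond the stated limit.

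Other limits also stand:

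- The dosing-time rule protects ECGs where a dosing time is recorded. ECGs are centrally read and unscheduled ones are grouped in 15-minute windows, so a missing day is unlikely for them.
- When the true pre-dose value falls on the start day, an order flag or label, or the preference for central over local laboratories, can keep the right baseline.
- A partial-dated record that was in fact taken before the first dose is correctly left eligible.
- The analyses are descriptive, and all laboratory values appear with their grades in a listing.

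A reader might infer that every partial-dated assessment in the start month or year becomes baseline. The restriction, the ECG rule and the same-day tie rules do not support that. A reader might also infer that the error always hides toxicity. Step 6 shows otherwise, and section 2.7.3 assesses several analytes in both directions, so one misplaced baseline can lower one shift and raise the other.

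**Conclusion.** The SAP contradicts itself on whether imputed dates apply to assessments, and one of the two readings can corrupt baseline. If Table 4-1 is applied as headed, an on-treatment lab value or vital sign, or an ECG with no recorded dosing time, can displace an earlier pre-dose value and leave the post-baseline data. When that value is abnormal, shifts and changes from baseline are understated in laboratory and ECG outputs that belong to the primary endpoint. When it is better than the true baseline, the distortion runs the other way.

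The effect on a single affected patient can be large (grade 3 to 2 instead of 0 to 3; −5 ms instead of +65 ms), but these are constructed cases. The SAP gives no count of partial-dated assessments; it is probably small, so the overall effect is unknown. The conclusion assumes that assessments carry no stop date and that the true baseline is dated before the start day. The point should be corrected, mainly because the correction costs so little.

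**What to change.** 1. Remove LB, EG and VS from Table 4-1, and safety assessments from the section 4.1.2 title, so that both agree with the restriction after Table 4-2.
2. Add to the baseline definition in section 2.1.1 that an assessment with a partial date is not eligible as baseline unless its known date part, visit label or sequence shows that it was taken before the first dose.
3. State that other partial-dated assessments are placed by visit label or sequence where possible, and are otherwise flagged in the listing.
4. State whether records that cannot be placed count as post-baseline in the worst-value tables. This is for the sponsor to choose: counting them risks reporting a pre-dose abnormality as on-treatment, and omitting them risks losing a real one.

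The cost is a few sentences and a small programming change. No new data are needed.
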